### **5.2.6.2. Dose-Limiting Toxicity**

A DLT will be defined as an AE or abnormal laboratory value that occurs within the first 28 days of treatment with KPT-9274, except for those that are clearly and incontrovertibly due to underlying disease, disease progression, or extraneous causes, and meets any of the criteria for defining dose-limiting toxicities as described in the table below. The CTCAE, Version 5.0 will be used for grading. In addition,  $> 3$  missed (consecutive or nonconsecutive) doses of KPT-9274 in the first 28 days due to a drug related toxicity will be considered to be a DLT.

Other events may occur which do not meet the definition of a DLT but are of concern to the Investigators may be considered to be DLTs.

**Table 6 Criteria for Defining Dose-Limiting Toxicities in AML Patients**

Toxicity	Any of the following criteria (based on CTCAE [Version 5.0]), with the exception of events that are clearly and incontrovertibly due to underlying disease, disease progression or extraneous causes:
Non-Hematologic	Grade 3 AST (SGOT) or ALT (SGPT) for $\geq 7$ days or grade 3 direct hyperbilirubinemia for $>7$ days
	Grade 2 AST (SGOT) or ALT (SGPT) accompanied by grade 2 direct hyperbilirubinemia
	All other clinically significant non-hematological $\geq$ grade 3 AEs with the following exceptions:
	
 
Grade 3 nausea, vomiting or diarrhea will be considered DLT only if not controlled with optimal therapy after 72 hours; however, if these AEs require hospitalization, total parenteral nutrition or tube feeding, they will be considered DLTs regardless of the time required for recovery.
 
<math>\geq</math> Grade 4 nausea, vomiting or diarrhea will be considered a DLT regardless of duration.
 
Grade<4 neutropenic fever
 
Grade 3 biochemical or electrolyte abnormalities may be considered exceptions to the DLT criteria only if they have no clinical consequences and resolve with appropriate management within 72 hours
 

	Any grade AE that is related to KPT-9274 that results in permanent discontinuation of therapy
	Any death related to KPT-9274
Hematologic	$\geq$ Grade 3 anemia, neutropenia and/or thrombocytopenia lasting for $\geq 28$ days from cycle 1 day 1 in the absence of residual AML (<5% blasts by morphology or detectable disease by immunohistochemistry and/or flow cytometry or other methods)

CTCAE Version 5.0 will be used for grading AEs and laboratory abnormalities. Patients may receive supportive care as per local institutional guidelines.
	

### 5.2.7. Dose Schedule for Evaluation During the Dose Expansion Phase

After completion of the Dose Escalation, Dose Expansion in up to 10 additional patients who meet the inclusion/exclusion criteria may be conducted to further explore safety, tolerability and preliminary evidence of anti-tumor activity of the RP2D of KPT-9274.

### 5.2.8. KPT-9274 Dose Reduction Guidelines for Toxicity

Prior to achieving a morphologic remission, KPT-9274 will not be held for any toxicities that are not attributable to KPT-9274.

After patients have achieved a morphologic remission, dose adjustments of KPT-9274 are permitted for those who do not tolerate the protocol-specified dosing schedule. The criteria for dose modifications of KPT-9274 for toxicities are outlined in [Table 10](#).

If, after the DLT period, interruption of treatment is required and this results in the resolution of the event, treatment will be resumed at the same dose. If after re-introduction the same toxicity reoccurs with the same severity, treatment re-initiation can resume at 25% of the current dose if the AE recovers to  $\leq$  grade 1 or baseline within 28 days. Patients who do not recover (i.e.,  $\leq$  Grade 1 or baseline) within 28 days of discontinuation of study treatment will not be permitted to re-start study treatment and will be discontinued from the study.

In the event of a DLT (Cycle 1) during the Dose Escalation Phase the patient must discontinue KPT-9274.

In the event of any other possibly related, likely related or related toxicity ( $\geq$  Grade 3) during the Dose Escalation Phase after a patient has achieved a morphologic remission, one of the following actions may be taken at the Investigator's discretion:

- Patients can continue treatment with KPT-9274 without a dose delay or reduction.
- If the decision is made to hold KPT-9274:
  - Patients may be re-started on KPT-9274 either at the original dose OR at 25% of the dose upon recovery to Grade  $\leq$  1 or baseline (see Table 9 for pre-specified dose modifications for AEs and Table 10 for dose modification guidelines for KPT-9274).

#### **5.2.8.1. Conditions Not Requiring KPT-9274 Dose Reduction**

The following conditions are exceptions to the dose-modification guidelines. KPT-9274 does not need to be held in the following cases:

- Alopecia of any grade
- Electrolyte or serum analyte (e.g., urate) abnormalities that are reversible with standard interventions
- Anemia

**Table 7 KPT-9274 Dose Modification and Supportive Care Guidelines**

Toxicity and Intensity	Dose Modification
Non-hematologic Toxicity	
Grade 1	Maintain dose. Consider instituting supportive care medications per institutional guidelines.
Grade 2	Institute supportive care medications per institutional guidelines.  If modifications are desired, guidelines for AEs $\geq$ Grade 3 should be followed. At the Investigator's discretion, patients may continue on KPT-9274 uninterrupted at their current dose.
$\geq$ Grade 3	Optimal supportive care medications according to institutional guidelines should be instituted.  Hold KPT-9274 until the event resolves to $\leq$ Grade 1 or baseline (as appropriate): 
 
First occurrence of <math>\geq</math> Grade 3:               
 
If supportive care results in the AE improving to Grade <math>\leq</math> 1 or baseline within 3 days, restart KPT-9274 at the current dose.
 
If the improvement to Grade <math>\leq</math> 1 or baseline takes longer than 3 days, KPT-9274 should be resumed at 25% of the dose.
 
 
 
Second or greater occurrence of <math>\geq</math> Grade 3, restart KPT-9274 at 50% of the dose upon improvement to Grade <math>\leq</math> 1 or baseline irrespective of duration.
 
 **If the toxicity does not resolve to $\leq$ Grade 1 or baseline within 28 days, study treatment will be discontinued permanently.
Hematological Toxicity for AML Patients	
AML patients typically have abnormal peripheral blood counts at diagnosis; myelosuppression is an expected event during the course of any therapy. Therefore, no dose adjustments or treatment interruption for hematological toxicity will occur during the first cycle or at any cycle in the presence of residual AML. Dose adjustments and/or treatment interruptions for hematological toxicity will be considered after the first cycle, in the absence of residual disease, according to the following guidelines:	

 
Patients in morphological remission (<5% blasts in the bone marrow by morphology, immunohistochemistry or flow cytometry) with pre-cycle ANC <math>>1 \times 10^9/L</math>, platelets <math>>50 \times 10^9/L</math> and hemoglobin <math>\geq 9.0 \text{ g/dL}</math> who have sustained neutropenia (ANC <math><0.5 \times 10^9/L</math>), anemia (hemoglobin <math>\leq 7.0 \text{ g/dL}</math>) or thrombocytopenia (platelets <math><20 \times 10^9/L</math>) for more than two consecutive weeks in the current cycle may hold KPT-9274, with growth factors per institutional policies, until the ANC recovers to <math>\geq 1 \times 10^9/L</math>, hemoglobin recovers to <math>\geq 9.0 \text{ g/dL}</math> and platelets recover to <math>\geq 50 \times 10^9/L</math>.
 
Patients in morphological remission (<5% blasts in the bone marrow by morphology, and no detectable disease by immunohistochemistry and/or flow cytometry or other methods) with pre-cycle ANC <math><1 \times 10^9/L</math>, hemoglobin <math>\leq 7.0 \text{ g/dL}</math> and platelets <math><50 \times 10^9/L</math> may continue KPT-9274 regardless of neutrophil, red blood cell or platelet count, with supportive care as needed.
 
Patients with active or residual disease (>5% blasts in the bone marrow by morphology, immunohistochemistry and/or flow cytometry or other methods) may continue treatment regardless of neutrophil, red blood cell or platelet counts with supportive care as needed.
 
	

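### After the DLT period, section 5.2.8 and Table 7 give different restart doses for the same related Grade 3 or higher non-haematologic event, and Table 7 does not say what its percentages are taken from

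*Combined protocol and SAP*

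**What the plan says.** Two places in the protocol set the restart dose after a held non-haematologic toxicity.

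**Section 5.2.8, general paragraph.** Once the DLT period is over, if "interruption of treatment is required and this results in the resolution of the event, treatment will be resumed at the same dose". No recovery time is attached. The paragraph continues: "If after re-introduction the same toxicity reoccurs with the same severity, treatment re-initiation can resume at 25% of the current dose", provided the event recovers within 28 days.

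**Section 5.2.8, discretion bullets.** For other related events of Grade 3 or higher "during the Dose Escalation Phase after a patient has achieved a morphologic remission, one of the following actions may be taken", at the investigator's discretion. One action is to carry on with neither delay nor reduction. The other is to hold, after which "Patients may be re-started on KPT-9274 either at the original dose OR at 25% of the dose upon recovery to Grade" 1 or lower, or baseline.

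**Table 7, Grade 3 or higher row.** The row directs "Hold KPT-9274 until the event resolves to" Grade 1 or lower, or baseline. For a first event that recovers "within 3 days, restart KPT-9274 at the current dose". If recovery "takes longer than 3 days, KPT-9274 should be resumed at 25% of the dose". For a second or later event, "restart KPT-9274 at 50% of the dose upon improvement to Grade" 1 or lower, or baseline, however long recovery took. Treatment stops for good if recovery takes more than 28 days.

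**Pointers.** Section 5.2.8 names the dose-modification table as the source of the criteria and refers to it again at the end of the bullets. Section 5.5 does the same. All three call it Table 10, its number in the list of tables; in the body it is captioned Table 7. The bullets also cite a Table 9 for pre-specified modifications, but in the body Table 9 is the causality classification.

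**The concern.** For one and the same event, a reader of the 5.2.8 paragraph and a reader of Table 7 can arrive at different doses, each with protocol text in support. Section 1.2.1 reports that adverse events in the earlier study were largely dose dependent, so the restart dose is a safety matter.

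Table 7 also has a difficulty of its own. It speaks of the current dose for a fast-recovering first event, but only of the dose, with no base, in both percentage steps. On one natural reading, a patient restarts higher after a second serious toxicity than after the first.

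What is at stake is dosing, exposure and tolerability after Cycle 1. Section 5.2.6.1 bases the RP2D on all safety data, including serious events after the DLT window. Section 8.1 pools escalation patients treated at the RP2D with the expansion patients for safety and efficacy. Mixed restart practice would make both harder to interpret.

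**Working it through.** **Inputs.** Dose levels are 20, 30, 40, 60, 80 and 100 mg (dose escalation table). Tablets are 5 mg and 20 mg (section 5.1.1), swallowed whole (section 5.2.4). The restart rules are those quoted above. The plan gives no figure of its own to reproduce.

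**Scope.** A related Grade 3 or higher non-haematologic event after the DLT period that recovers within 28 days. Section 5.2.8 opens dose adjustment to patients in morphologic remission.

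**Step 1: first event.** If it recovers within 3 days, both sources give 100% and there is no conflict. If it takes longer, the paragraph gives 100% and Table 7 gives 25%.

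**Step 2: recurrence while on full dose** (Table 7 reaches this after a fast first event). The paragraph permits 25% of the current dose for the same toxicity at the same severity. Table 7 directs 50% for any second or later event.

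Restart dose = assigned dose × stated share, in mg:

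| Assigned dose | 20 | 30 | 40 | 60 | 80 | 100 |
|---|---|---|---|---|---|---|
| Slow first event, 5.2.8 paragraph (100%) | 20 | 30 | 40 | 60 | 80 | 100 |
| Slow first event, Table 7 as written (25%) | 5 | 7.5 | 10 | 15 | 20 | 25 |
| Slow first event, Table 7 if 25% is the cut (75%) | 15 | 22.5 | 30 | 45 | 60 | 75 |
| Recurrence on full dose, 5.2.8 as written (25%) | 5 | 7.5 | 10 | 15 | 20 | 25 |
| Recurrence on full dose, Table 7 (50%) | 10 | 15 | 20 | 30 | 40 | 50 |

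- Slow first event: 100/25 = 4.0 as written; 100/75 = 1.33 if 25% is the cut.
- Recurrence on full dose: 50/25 = 2.0 as written, with Table 7 now the higher. So neither source is uniformly the more cautious. If 25% is the cut in 5.2.8 too, the comparison is 75% against 50%, or 1.5-fold the other way.

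**Step 3: Table 7 alone.** A slow first event followed by a recurrence, starting from 80 mg:

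| Meaning of the percentage | Base | Sequence (mg) |
|---|---|---|
| Share remaining | Assigned dose | 80, 20, 40 |
| Share remaining | Current dose | 80, 20, 10 |
| Size of cut | Assigned dose | 80, 60, 40 |
| Size of cut | Current dose | 80, 60, 30 |

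Only the first reading raises the dose after the second event (40/20 = 2.0), but nothing in the text excludes it.

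**Step 4: phases.** In escalation after remission, the bullets allow the original dose or 25%, so either first-event dose is permitted. They also allow continuing without a hold, which Table 7 does not, and they do not offer its 50% step. They do not reach the expansion phase. Table 7's own discretion line sits in its Grade 2 row. In expansion, therefore, the paragraph and the table meet with no clause between them.

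**Step 5: tablets.** At the 30 mg level, 25% is 7.5 mg and 75% is 22.5 mg. Neither can be made from whole tablets. Section 5.3 refers to a Pharmacy Manual, which is not among the documents and may give a rounding rule.

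**The case against.** The best answer is that the table governs. Sections 5.2.8 and 5.5 both send the reader to it for dose modification, and in escalation its 3-day test could serve as the rule for choosing between the two doses in the bullets. The same-dose sentence could then be read as filling a real gap: Table 7's haematologic guidance allows a hold but states no restart dose. This is a sensible reconciliation, but no sentence adopts it. The paragraph is not limited to haematologic events and does not defer to the table.

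Other parts of the objection stand and limit the point:

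- The 5.2.8 recurrence rule is permissive and confined to the same toxicity at the same severity. The two-fold gap therefore sets an option against an instruction, and is weaker than the first-event conflict.
- The escalation bullets are an express grant of discretion. A reader might infer a direct contradiction over the first-event dose in both phases. In escalation after remission the bullets permit either dose, so the direct conflict is in the expansion phase, which is optional and adds up to 10 patients.
- The order 25% then 50% suggests that cuts of those sizes may have been intended. A reader might infer that Table 7 plainly doubles the dose after a second toxicity. That holds only if the percentages are remaining shares of the assigned dose, which the documents neither state nor rule out.

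**Conclusion.** The point holds. For a slow-recovering first event, the 5.2.8 paragraph and Table 7 differ four-fold as written, or 1.33-fold if 25% is the size of the cut. The conflict is direct in expansion. In escalation it is confined to whether a hold is required and to the missing 50% step. Table 7's unnamed base allows a reading in which the dose rises after a second serious toxicity.

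A reader might go further and infer harm to dose finding or to the response rate. The documents do not support that. A Cycle 1 DLT in escalation requires discontinuation, so the restart rules leave the DLT count and the MTD alone. Patients in morphologic remission will mostly have met a response category in Appendix 2 already, so ORR is largely unaffected. Exposure, later safety, and the descriptive duration and survival endpoints could be affected. The documents give no rate for such events; the affected group is probably small. This should be fixed because a wrong dose can follow from reading the plan as written, and the remedy is cheap.

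**What to change.** 1. State that Table 7 governs non-haematologic toxicity in both phases, and align the 5.2.8 paragraph with it. One way is to limit the same-dose restart to first events that recover within 3 days and to haematologic holds.
2. Either keep the escalation-phase option to continue without a hold as a stated exception in Table 7, or remove it.
3. Have the sponsor confirm whether 25% and 50% are the remaining dose or the size of the reduction, and name the base dose for each step.
4. Require each recurrence to restart below the dose at which it occurred, and treatment to stop if no lower dose can be given. For example, a recurrence on 5 mg has no lower whole-tablet dose.
5. Once item 3 is settled, list the resulting doses for each level in whole 5 mg steps. Doing so earlier would fix an unconfirmed reading.
6. Correct the stale references: Tables 9 and 10 in section 5.2.8, and Table 10 in section 5.5.

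The cost is a text amendment and somewhat less investigator discretion. No patients, visits or procedures are added.

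### Table 7 restarts at 25% after a slow first Grade 3 or higher event but at 50% after a second, with no stated base dose, and Section 5.2.8 gives different restart doses

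*Combined protocol and SAP*

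**What the plan says.** Table 7, the dose modification and supportive care table, has three restart rules for a non-hematologic event of Grade 3 or higher. (Sections 5.2.8 and 5.5 cite this table as Table 10, its number in the list of tables.)

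- First event, improved within 3 days: "restart KPT-9274 at the current dose".
- First event, slower improvement: "KPT-9274 should be resumed at 25% of the dose".
- Second or later event, whatever its duration: "restart KPT-9274 at 50% of the dose upon improvement to Grade" 1 or lower, or to baseline.

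Only the first rule names the current dose as its base. The other two do not say which dose the percentage applies to.

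Section 5.2.8 has rules of its own.

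- After the DLT period, if "interruption of treatment is required and this results in the resolution of the event, treatment will be resumed at the same dose". This makes no distinction by grade or by speed of recovery, short of the 28-day limit.
- "If after re-introduction the same toxicity reoccurs with the same severity, treatment re-initiation can resume at 25% of the current dose", given recovery within 28 days.
- In the Dose Escalation Phase, for an at least possibly related Grade 3 or higher event after morphologic remission, the investigator may continue unchanged or hold the drug. After a hold: "Patients may be re-started on KPT-9274 either at the original dose OR at 25% of the dose upon recovery to Grade" 1 or lower, or baseline.

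Some clauses limit when these rules apply. "After patients have achieved a morphologic remission, dose adjustments of KPT-9274 are permitted"; "In the event of a DLT (Cycle 1) during the Dose Escalation Phase the patient must discontinue KPT-9274"; and in both places an event not recovered by 28 days ends treatment. Sections 5.2.8 and 5.5 refer to the table for dose modification. Neither says which text prevails where they differ.

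**The concern.** A restart schedule for severe toxicity should give one dose for one event, and that dose should not rise as events accumulate. Table 7 fails the second test: its percentage is higher after the second event than after a slow first one. Because the base is not stated, the investigator cannot tell whether the patient is meant to go up or down. Read with 5.2.8, the schedule also fails the first test, because the same recurrence or the same slow first event can have two restart doses.

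This is a patient-safety instruction. Section 1.2.1 reports that adverse events in the completed study were largely dose dependent, so a twofold or larger difference in restart dose is not trivial. Section 5.2.6.1 also draws on serious events after the DLT window when the RP2D is chosen, so dosing after Cycle 1 forms part of that evidence. The size of any such effect cannot be worked out from the documents.

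**Working it through.** The plan gives no restart doses in mg, so there is no figure of its own to reproduce. The check compares the rules and then turns them into doses.

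**Inputs.** Assigned dose D = 20, 30, 40, 60, 80 or 100 mg (dose escalation table; 20 mg is the optional de-escalation level). Tablets are 5 mg and 20 mg (Section 5.1.1) and are swallowed whole (Section 5.2.4), so a dose that can be made is a multiple of 5 mg. Restart fractions are those listed above.

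**Step 1: Table 7 alone, slow first event, then a second event.**

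- First restart: 0.25 × D.
- Second restart, assigned-dose base: 0.50 × D. Ratio to the dose just taken: 0.50D / 0.25D = 2.
- Second restart, current-dose base: 0.50 × 0.25D = 0.125D. Ratio to the dose just taken: 0.125D / 0.25D = 0.5.

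| D (mg) | 0.25D | 0.50D | 0.125D |
|---|---|---|---|
| 20 | 5 | 10 | 2.5 |
| 30 | 7.5 | 15 | 3.75 |
| 40 | 10 | 20 | 5 |
| 60 | 15 | 30 | 7.5 |
| 80 | 20 | 40 | 10 |
| 100 | 25 | 50 | 12.5 |

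The two readings of the base differ by a factor of 0.50 / 0.125 = 4. If the first restart was at full dose, the second-event rule lowers the dose on either base, so the rising path needs a 25% first restart.

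**Step 2: Table 7 against 5.2.8, same toxicity recurring at the same severity after a full-dose restart.** Table 7 gives 0.50D; 5.2.8 allows 0.25D. Ratio 2, for example 20 mg against 10 mg in the 40 mg cohort.

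**Step 3: Table 7 against 5.2.8, first event after the DLT period that takes more than 3 days to improve.** Table 7 gives 0.25D; the general sentence in 5.2.8 gives D. Ratio 4, for example 15 mg against 60 mg in the 60 mg cohort. For escalation patients in remission with a related event, the later bullet in 5.2.8 allows the original dose or 25%. These match Table 7's two first-event branches, so the difference is largely accommodated there. It remains for expansion patients (up to 10, if that phase is run) and for cases outside the bullet, such as events before remission. The bullet never offers 50%, so it does not accommodate Table 7's second-event rule.

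**Step 4: can the doses be made?** 0.25D is a multiple of 5 mg at every level except 30 mg, where it is 7.5 mg. At a first reduction from full dose the assigned and current doses coincide, so this does not depend on the base. 0.50D can be made at every level. 0.125D can be made only at 40 and 80 mg; this matters only if the current-dose base is intended.

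**The case against.** The strongest reply is that the table governs. Two sections send the reader to it, and a specific rule for Grade 3 or higher naturally overrides a general sentence about interruptions. The recurrence sentence in 5.2.8 is permissive, and the escalation bullet contains the table's two first-event doses. On that view only a loosely worded row and one stray sentence remain. Most of this is fair, and it is why the first-event difference should not be counted against escalation patients in remission. But no precedence is stated, and preferring the table does not repair the table: the 25%-then-50% order and the missing base are inside it.

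Three stronger readings are tempting.

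- A reader might infer that the protocol orders a doubling of the dose after severe toxicity. It does not. That outcome needs a slow first event that did not end treatment, a 25% restart, a second Grade 3 or higher event recovering within 28 days, and the assigned-dose base. Even then the result is half the assigned dose. In escalation after remission the investigator may choose otherwise, and Section 4.2 allows removal for unacceptable toxicity in any phase.
- A reader might infer that dose finding is compromised. The Cycle 1 DLT counts and the MTD rule do not use these restart doses, and a DLT in escalation stops the drug.
- A reader might infer that 25% is a slip for a reduction by 25%. The phrasing at 25% occurs twice in 5.2.8 and once in Table 7, so the text gives no ground for correcting it unaided.

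Nor can reach be bounded by the 72-hour limits in Table 6. They apply only to the gastrointestinal and the biochemical or electrolyte exceptions; the transaminase criterion uses 7 days.

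**Conclusion.** The point stands as a defect of wording with safety consequences. Table 7's row for non-hematologic Grade 3 or higher events is not usable as written. After a 25% restart, a second event leads to either twice the dose just taken or 12.5% of the assigned dose. Section 5.2.8 adds a twofold difference on equal recurrence. It also adds a fourfold difference on a slow first event, mainly for expansion patients and cases outside the escalation bullet. The 7.5 mg dose at the 30 mg starting level cannot be made.

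This assumes that doses come only from whole tablets of the two stated strengths; the Pharmacy Manual cited in Section 5.3 is not available and might add dispensing detail. It also takes the percentages as printed. The documents do not allow an estimate of how many patients would meet these rules. The sponsor should correct this, but it does not threaten the trial's primary result.

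**What to change.** Amend Table 7 and Section 5.2.8 together.

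1. Define the base of every percentage as the assigned dose or the current dose.
2. State one non-increasing sequence in Table 7, so that the restart after a second or later Grade 3 or higher event never exceeds the dose taken before it.
3. Make three rules in 5.2.8 follow Table 7 in both phases: the same-dose sentence, the recurrence sentence, and the bullet offering the original dose or 25%.
4. Print the restart doses in mg for each cohort, as multiples of 5 mg.

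The sponsor should confirm the intended percentages. If a reduction by 25% was meant, which is only an assumption, the first reduced dose would be 0.75D = 15, 22.5, 30, 45, 60 and 75 mg. The next would be 0.50D = 10, 15, 20, 30, 40 and 50 mg. That sequence falls at every level, but 22.5 mg would need rounding to 20 or 25 mg.

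The cost is an amendment to one table and one section, with no added patients, visits or tests.
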